- To assess immunologic predictors of virologic response (all subjects) and relapse (among subjects with confirmed AdV clearance from plasma)
- To evaluate exploratory biomarkers for BCV-related gastrointestinal (GI) toxicity (e.g., citrulline, suppression of tumorigenicity-2 [ST2], T cell immunoglobulin mucin-3 [TIM3], and C-reactive protein [CRP])
- To assess healthcare resource utilization

Methodology: This is a randomized, open-label, multi-center study of the safety, overall tolerability, and antiviral activity of BCV, as compared with SoC, in pediatric recipients of high-risk (i.e., T cell-depleted) allogeneic HCT. Pediatric patients with AdV detected in plasma within the previous 21 days and for the first time since their qualifying transplant may be screened for participation in the study. Subjects who meet all applicable entry criteria will be randomized in a 2:1 ratio to receive either BCV or SoC. The day of randomization is defined as Day 1. During randomization, subjects will be stratified based on the following variables: last (non-baseline) screening AdV viremia ($\geq 10,000$ copies/mL vs. $< 10,000$ copies/mL), time from transplant to randomization (≥ 28 days vs. < 28 days), and T cell-depletion methodology (receipt of alemtuzumab or ex vivo depletion vs. receipt of anti-thymocyte globulin [ATG]). Subjects randomized to receive BCV will be treated until AdV deoxyribonucleic acid (DNA) is confirmed to be undetectable in plasma, up to a maximum of 16 weeks post-randomization. Subjects randomized to the SoC arm will be managed according to local or institutional practice guidelines for the treatment of AdV infection. All subjects, regardless of treatment assignment, will be followed in the study for a total of 36 weeks post-randomization. Subjects will be assessed on a weekly basis through Week 16, with additional assessments performed at Weeks 24 and 36 post-randomization. The data collected through Week 16 will comprise the primary data set for the study; hence, the primary database will be locked and analyzed following capture of data for all subjects through Week 16. In addition, all subjects (both BCV and SoC recipients) will be encouraged to enroll in the BCV Registry (Study CMX001-333) to assess the longer-term impact of exposure to BCV.

Number of Subjects (Planned):

The study will target the enrollment of a total of approximately 141 subjects, with 94 subjects randomized to the BCV arm and 47 subjects randomized to the SoC arm.

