Assuming the observed standard deviation of $\sim 1.03 \log_{10}$ copies/mL in AAUC at Week 16 from a comparable subset of SoC subjects, the study has $> 90\%$ power with the currently planned sample size to demonstrate superiority of BCV vs. SoC, given that the true difference in means is $> 0.6 \log_{10}$ copies/mL (i.e., an effect size of ~ 0.58). In addition, the overall mortality at Week 16 non-inferiority comparison will have $> 80\%$ power in the event that the expected mortality for SoC is 20% to 30% and there is a true mortality advantage of 6% to 9% in favor of BCV ([Feghoul 2015](#), [Hiwarkar 2017](#), [Mynarek 2014](#)).

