The study will also provide a holistic assessment of safety that includes the known side effects of oral BCV (GI toxicity) and IV CDV (renal injury). Immunosuppressant therapies utilized in the study will be recorded to document that short course BCV therapy and updated safety management guidance has mitigated the overuse of steroids observed in the CMX001-301 study (Section 4.2.3.1). Though it is anticipated that control of AdV replication will limit resulting organ damage and numerically improve survival in patients treated with oral BCV, a non-inferiority analysis of overall mortality at Week 16 between the BCV and SoC arms is included as a key secondary efficacy endpoint in order to rule out an untoward effect of BCV on outcomes.

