12. STATISTICS

All summaries and analyses will be presented in tabular or graphical form. Statistical methods will be described in detail in the Statistical Analysis Plan (SAP), which will be initially finalized as soon as possible during study enrollment with subsequent amendments clearly documenting changes to the plan throughout the study. No amendments to the SAP will be made after the database lock for the primary analysis and subsequent changes will be presented as post hoc analyses. All statistical analyses will be conducted using SAS[®] software, unless otherwise specified in the SAP.

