12.1. Determination of Sample Size

A total of approximately 141 subjects will be enrolled into this study. Sample size calculations were based on the primary endpoint, i.e., AAUC through Week 16. Assuming the observed standard deviation of 1.03 log₁₀ copies/mL in AAUC at Week 16 from a comparable subset of SoC subjects, the study has > 90% power with the currently planned sample size to demonstrate superiority of BCV vs. SoC, given that the true difference in means is > 0.6 log₁₀ copies/mL (i.e., an effect size of ~ 0.58). In addition, the overall mortality at Week 16 non-inferiority comparison will have > 80% power in the event that the expected mortality for SoC is 20% to 30% and there is a true mortality advantage of 6% to 9% in favor of BCV ([Feghoul 2015](#), [Hiwarkar 2017](#), [Mynarek 2014](#)).

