12.4. Efficacy Analyses

12.4.1. Primary Efficacy Endpoint

The primary AAUC analysis will utilize all randomized subjects (ITT) in an analysis of covariance (ANCOVA) with all stratification factors included in the model: T cell-depletion method (alemtuzumab or ex vivo cell selection vs. ATG), time from HCT to randomization (< 28 days vs. \geq 28 days), and baseline AdV viremia (continuous \log_{10} copies/mL). These stratification factors have been selected as those that are clearly related to time to immune reconstitution (time from HCT to confirmed AdV viremia > 1000 copies/mL and thus randomization, procedural differences in depth and duration of immune suppression by T cell-depletion method) with resulting expected differences in clearance of viremia, and/or association with mortality (peak viral load). Regarding baseline AdV viremia, subjects will be stratified at the time of randomization according to \geq 10,000 vs. < 10,000 copies/mL; however, this factor will be included in the analysis as a continuous covariate in order to improve power in determining a treatment effect. In the ANCOVA, AdV viremia values that are undetectable will be imputed at 99 copies/mL (i.e., one less than the lower limit of detection of 100 copies/mL) and values that are detected, but not quantifiable (BLQ) will be imputed at 189 copies/mL (i.e., one less than the lower limit of quantification of 190 copies/mL).

Subjects who die or are lost to follow-up (i.e., drop-outs) prior to Week 16 are accounted for inherently in the AAUC approach by truncating their follow-up period, thereby normalizing AUC over time of follow-up (Li 2012). It should be noted that subjects lost to follow-up are anticipated to be zero or negligible, and approximately 16% to 24% of subjects are expected to die by Week 16. Regardless, the primary analysis will be supplemented by a number of planned sensitivity analyses to assess the impact of subjects who die prior to Week 16 and other potential influential elements on the primary inference and to allow for a more comprehensive assessment of efficacy.

The first three approaches are proposed to account for these subjects in a typical missing data framework:

- Jump to reference imputation, where the missing part of the trajectory is imputed from the control group average ([Kenward 2015](#)).

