- Multiple imputation, where the missing part of the trajectory is imputed based on a model ([Rubin 1978](#)). This imputation is repeated to create multiple simulated data sets (e.g., 5-times the number of deaths plus drop-outs). Each of these simulated data sets is analyzed independently and the results from these analyses are pooled to yield a final inference.
- Undetectable imputation, where the missing part of the trajectory is imputed as undetectable.

In addition to the above, three other supportive analyses are proposed to directly account for subjects who die prior to Week 16:

- Baseline imputation, where the missing part of the trajectory for deaths only is imputed at the baseline value for the subject.
- Analysis of time below the detection limit, whereby subjects who die are considered to be above the detection limit after death. This approach will be repeated using time below 1000 copies/mL, which is a clinically-meaningful level of viremia often signaling viral control vs. need to address in clinical practice.
- Generalized pairwise comparisons of prioritized outcomes ([Buyse 2010](#)). In this approach, all BCV subjects are compared with all SoC subjects in the same stratum. Comparisons will be made based on the following hierarchy:
 - Alive or dead at Week 16
 - If both die before Week 16, compare time to death
 - If both are alive at Week 16, compare AAUC

Each comparison yields a favorable, unfavorable, or neutral result. The “proportion in favor of treatment” (Δ) is the net difference between the number of favorable pairs and the number of unfavorable pairs divided by the total number of pairs. The null hypothesis $H_0: \Delta=0$ is tested using a randomization test.

Another important factor that may influence the primary inference is the imputation of undetectable and BLQ AdV viremia values, with additional sensitivity analyses conducted in order to assess the potential impact of this imputation:

- Impute all undetectable/BLQ values at 1 copy/mL (i.e., 0 log₁₀ c/mL)
- Impute all undetectable/BLQ values at 189 copies/mL
- Impute all values < 1000 copies/mL at 1 copy/mL

In addition, a supportive analysis of overall mortality (adjusting for advanced baseline disease, [Matthes-Martin 2008](#)) will examine the non-inferiority of BCV treatment to SoC. No negative impact on mortality will be concluded if the upper bound of the one-sided 95% confidence

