interval (CI) for the absolute difference between BCV mortality and SoC mortality is $< 10\%$. The proposed sample size will have $> 80\%$ power to demonstrate this conclusion, assuming SoC mortality in the expected range of 20% to 30% and a risk difference of 6% to 9% in favor of BCV (Feghoul 2015, Hiwarkar 2017, Mynarek 2014). In the event this supportive analysis concludes non-inferiority and the primary endpoint is met, superiority for overall mortality at Week 16 will be tested at alpha 0.05. Non-relapse mortality will be assessed in a similar fashion.

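### The stated > 80% power for Week 16 mortality non-inferiority holds on one unstated pairing of rates with a score-type bound; as worded, with any advantage at any SoC rate, it does not

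*Combined protocol and SAP*

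**What the plan says.** Section 12.1 states that "the overall mortality at Week 16 non-inferiority comparison will have > 80% power in the event that the expected mortality for SoC" lies between 20% and 30%, with an advantage of 6% to 9% for BCV. The Synopsis repeats the condition ("the expected mortality for SoC is 20% to 30% and there is a true mortality advantage of 6% to 9% in favor of BCV"), and Section 12.4.1 gives it again, "assuming SoC mortality in the expected range of 20% to 30% and a risk difference of 6% to 9% in favor of BCV". None of the three says how the two ranges pair, and none names the interval behind the power figure.

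The decision rule is in Section 12.4.1: "No negative impact on mortality will be concluded if the upper bound of the one-sided 95% confidence" interval for the absolute BCV-minus-SoC difference lies below 10%. The analysis adjusts for advanced baseline disease. The same section remarks, while discussing truncated follow-up in the AAUC analysis, that "approximately 16% to 24% of subjects are expected to die by Week 16". The Synopsis gives the arm sizes: "with 94 subjects randomized to the BCV arm and 47 subjects randomized to the SoC arm".

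Section 4.3.7 explains that the mortality comparison "is included as a key secondary efficacy endpoint in order to rule out an untoward effect of BCV on outcomes". On methods, Section 12 says: "Statistical methods will be described in detail in the Statistical Analysis Plan (SAP), which will be initially finalized as soon as possible during study enrollment".

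**The concern.** Two ranges joined by a plain conjunction read as a region in which the claim is true everywhere. A reader of Section 12.1 would take the chance of missing non-inferiority to be under 20% for any SoC rate from 20% to 30% with any advantage from 6 to 9 points. Power depends strongly on both quantities. A 6-point advantage is worth less at 30% SoC mortality than at 20%, because the variance grows while the distance to the margin stays at 16 points.

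This is the comparison meant to exclude harm on mortality, and passing it is one of two conditions for the superiority test on mortality in Section 12.4.1. If its power is overstated, a failure to show non-inferiority would look more surprising, and more adverse to BCV, than the design warrants.

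**Working it through.** **Inputs.** 94 BCV and 47 SoC subjects (Synopsis). Margin of 10 points and one-sided 95% upper bound (Section 12.4.1). SoC mortality 20% to 30%, BCV advantage 6 to 9 points (Synopsis, 12.1, 12.4.1). Losses to follow-up zero or negligible (12.4.1), so no inflation. No covariate adjustment is modelled, because the document gives no figures for it.

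**Step 1: the pairing.** Overall mortality is (94 × pB + 47 × pS)/141.
- 20%/14%: (13.16 + 9.40)/141 = 16.0%.
- 30%/21%: (19.74 + 14.10)/141 = 24.0%.

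These are exactly the ends of the 16% to 24% in Section 12.4.1. The implied line is pB = 0.7 × pS, a constant 30% relative reduction. Fully crossed ranges would instead give 14.0% (20%/11%) to 26.0% (30%/24%).

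**Step 2: power by the unpooled normal formula.** Power = Φ((0.10 + pS − pB)/SE − 1.645), with SE = √(pS(1−pS)/47 + pB(1−pB)/94).
- 20%/14%: SE = √(0.16/47 + 0.1204/94) = 0.0684; Φ(0.16/0.0684 − 1.645) = 75.6%.
- 25%/19%: SE = √(0.1875/47 + 0.1539/94) = 0.0750; Φ(0.16/0.0750 − 1.645) = 68.7%.

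**Step 3: exact power.** All 95 × 48 binomial outcomes were enumerated, and the probabilities of those whose upper bound falls below 10 points were summed.

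| SoC/BCV (%) | Advantage (points) | Overall mortality (%) | Unpooled formula (%) | Exact Wald (%) | Exact Miettinen-Nurminen (%) |
|---|---|---|---|---|---|
| 20/14 | 6 | 16.0 | 75.6 | 78.5 | 81.1 |
| 25/17.5 | 7.5 | 20.0 | 76.1 | 78.0 | 80.8 |
| 30/21 | 9 | 24.0 | 77.7 | 78.9 | 81.7 |
| 25/19 | 6 | 21.0 | 68.7 | 70.1 | 73.4 |
| 28/22 | 6 | 24.0 | 65.6 | 66.3 | 69.9 |
| 30/24 | 6 | 26.0 | 63.8 | 64.3 | 67.8 |
| 20/11 | 9 | 14.0 | 88.6 | 91.7 | 93.1 |
| 25/16 | 9 | 19.0 | 82.5 | 84.9 | 87.0 |

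**Reading the table.** The first three rows are the implied line. The plan's figure reproduces there with the score-type bound: 80.8% to 81.7% along the whole line. Newcombe and Agresti-Caffo bounds also stay above 80% (lowest value 80.3%). Exact Wald gives 78.0% to 78.9%. The next three rows lie below the line, and all three methods miss 80%. The last two lie above it, and all three clear 80%.

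At a fixed 6-point advantage, 80% power is reached only up to an SoC rate of 17.4% (unpooled), 19.2% (exact Wald) or 20.7% (Miettinen-Nurminen). The smallest stated advantage therefore supports the claim only at the bottom of the SoC range, and only with the score-type bound.

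**Step 4: error rate at the margin.** With BCV mortality exactly 10 points above SoC and SoC at 20% to 30%, the exact one-sided error is 5.2% to 5.3% for Miettinen-Nurminen and 4.4% to 4.7% for Wald. Part of the score bound's extra power comes from this slightly larger error.

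**The case against.** The strongest reply is that the ranges were never meant as a free grid. The 16% to 24% overall mortality matches 20%/14% and 30%/21% to the decimal, and on that line a standard score bound delivers the stated power. This stands, and it is very probably what the sponsor computed. A reader might infer that the > 80% is simply an error, or that it fails over most of the planned scenarios. The document does not support that: the figure reproduces on the implied pairing, and even on the free grid 57% of combinations exceed 80% with the score bound (39% with exact Wald, 25% with the unpooled formula). Two illustrative pairs, 30%/24% and 20%/11%, fall outside the 16% to 24%.

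The reply does not dispose of the point. The overall mortality figure is not tied to the power statement, and it does not exclude weaker pairs: 25%/19% (21.0% overall) and 28%/22% (24.0%) satisfy every stated range, yet power there is 66% to 73% across the three methods.

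It is also fair to say that the bound may be named in the separate SAP, which is not part of the supplied document. The missing method is thus a gap in the power statement, not proof that the analysis is undefined. Finally, the planned adjustment for advanced disease might add power, and a Wald shortfall of 1 to 2 points might not survive it. The document gives no means of checking.

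**Conclusion.** The stated power is right on one pairing that the plan does not spell out, with one class of bound that the power statement does not name. On the implied line, unadjusted power is about 81% to 82% (score), 78% to 79% (exact Wald) or 76% to 78% (unpooled formula). Read as worded, it falls to about 70% to 73% at 25% vs 19%, 66% to 70% at 28% vs 22%, and 64% to 68% at 30% vs 24% (exact Wald to score). At 25% vs 19% the chance of missing non-inferiority is therefore about 27% to 30%, not under 20%.

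These figures assume 94 and 47 evaluable subjects, independent binomial outcomes and no covariate adjustment. The severity is minor to moderate: Section 12.1 bases the sample size on AAUC, and the margin and decision rule are unaffected. A reader might infer that the trial needs to be larger. That does not follow, because mortality power did not set the sample size.

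**What to change.** In the Synopsis, Section 12.1 and Section 12.4.1, replace the unqualified figure with a statement that names the pairing and the bound. With a score bound:

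> With 94 BCV and 47 SoC subjects, a 10-point margin and a one-sided 95% Miettinen-Nurminen upper bound, unadjusted power is about 81% for 20% vs 14% through 30% vs 21%, falling to about 73% at 25% vs 19% and 68% at 30% vs 24%.

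With a Wald bound:

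> With 94 BCV and 47 SoC subjects, a 10-point margin and a one-sided 95% Wald upper bound, unadjusted power is about 78% to 79% for 20% vs 14% through 30% vs 21%, falling to about 70% at 25% vs 19% and 64% at 30% vs 24%.

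Use the same type of bound in the analysis and name it in Section 12.4.1. If the separate SAP already names one, carry that over and use the matching text.

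The cost is wording in three places and no additional subjects. The stated power becomes slightly less favourable. The choice of bound is a trade-off: the score bound gains about 3 points of power but runs at 5.2% to 5.3% one-sided error at the margin, while Wald stays below 5%.

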12.2. Analysis Sets

All subjects will be classified into Intent-to-Treat (ITT), modified Intent-to-Treat (mITT), Per Protocol (PP), Safety, and PK analysis sets. The following definitions will be used:

- **ITT:** The ITT analysis set will include all subjects who are randomized.
- **mITT:** The mITT analysis set will include all subjects in the ITT analysis set with Adv viremia ≥ 1000 copies/mL measured by the designated central virology laboratory in the last sample on or prior to randomization. Subjects randomized to BCV and not treated will be excluded from the mITT analysis set.
- **PP:** The PP analysis set will include all subjects in the mITT analysis set who complete the study through Week 16 (or die prior to Week 16) and do not have any major protocol deviations (defined as significant inclusion/exclusion criteria violation or noncompliance that would be expected to impact the analysis of efficacy).
- **Safety:** The safety analysis set will include all subjects who are randomized to and receive at least one dose of BCV, and all subjects who are randomized to SoC.
- **PK:** The PK analysis set will include all subjects who are randomized to and receive at least one dose of BCV, and have at least one blood sample collected for analysis of plasma BCV concentrations.
- **Safety Exposure-Response:** The safety exposure-response analysis set will include subjects who are in both the safety analysis set and the PK analysis set.
- **Efficacy Exposure-Response:** The efficacy exposure-response analysis set will include subjects who are in both the mITT analysis set and the PK analysis set.

The ITT analysis set will be used to summarize all efficacy endpoints, including the primary endpoint/analysis. The mITT and PP analysis sets will be determined prior to database lock for the primary analysis, and will be used for supportive primary efficacy analyses and possibly other selected endpoints to be defined in the SAP. All efficacy analyses will use the randomized treatment assignment. The safety analysis set will be used for all safety analyses and the PK analysis set will be used for all PK analyses.

12.3. Interim Analyses

No formal interim analyses are planned. At least two safety reviews will be conducted by the DSMB. The first safety review will be performed after the first 30 subjects enrolled have completed through Week 16 (or have died or are lost to follow-up). The second safety review will be performed after the first 60 subjects enrolled have completed through Week 16 (or have died or are lost to follow-up). In addition, safety and safety-exposure response will be monitored by the DSMB periodically, as described in Section 4.5. There are no plans to stop the study for efficacy or futility; hence, no alpha-adjustment for DSMB monitoring is made.

12.4. Efficacy Analyses

12.4.1. Primary Efficacy Endpoint

The primary AAUC analysis will utilize all randomized subjects (ITT) in an analysis of covariance (ANCOVA) with all stratification factors included in the model: T cell-depletion method (alemtuzumab or ex vivo cell selection vs. ATG), time from HCT to randomization (< 28 days vs. \geq 28 days), and baseline AdV viremia (continuous \log_{10} copies/mL). These stratification factors have been selected as those that are clearly related to time to immune reconstitution (time from HCT to confirmed AdV viremia > 1000 copies/mL and thus randomization, procedural differences in depth and duration of immune suppression by T cell-depletion method) with resulting expected differences in clearance of viremia, and/or association with mortality (peak viral load). Regarding baseline AdV viremia, subjects will be stratified at the time of randomization according to \geq 10,000 vs. < 10,000 copies/mL; however, this factor will be included in the analysis as a continuous covariate in order to improve power in determining a treatment effect. In the ANCOVA, AdV viremia values that are undetectable will be imputed at 99 copies/mL (i.e., one less than the lower limit of detection of 100 copies/mL) and values that are detected, but not quantifiable (BLQ) will be imputed at 189 copies/mL (i.e., one less than the lower limit of quantification of 190 copies/mL).

Subjects who die or are lost to follow-up (i.e., drop-outs) prior to Week 16 are accounted for inherently in the AAUC approach by truncating their follow-up period, thereby normalizing AUC over time of follow-up (Li 2012). It should be noted that subjects lost to follow-up are anticipated to be zero or negligible, and approximately 16% to 24% of subjects are expected to die by Week 16. Regardless, the primary analysis will be supplemented by a number of planned sensitivity analyses to assess the impact of subjects who die prior to Week 16 and other potential influential elements on the primary inference and to allow for a more comprehensive assessment of efficacy.

The first three approaches are proposed to account for these subjects in a typical missing data framework:

- Jump to reference imputation, where the missing part of the trajectory is imputed from the control group average ([Kenward 2015](#)).
- Multiple imputation, where the missing part of the trajectory is imputed based on a model ([Rubin 1978](#)). This imputation is repeated to create multiple simulated data sets (e.g., 5-times the number of deaths plus drop-outs). Each of these simulated data sets is analyzed independently and the results from these analyses are pooled to yield a final inference.
- Undetectable imputation, where the missing part of the trajectory is imputed as undetectable.

In addition to the above, three other supportive analyses are proposed to directly account for subjects who die prior to Week 16:

- Baseline imputation, where the missing part of the trajectory for deaths only is imputed at the baseline value for the subject.
- Analysis of time below the detection limit, whereby subjects who die are considered to be above the detection limit after death. This approach will be repeated using time below 1000 copies/mL, which is a clinically-meaningful level of viremia often signaling viral control vs. need to address in clinical practice.
- Generalized pairwise comparisons of prioritized outcomes ([Buyse 2010](#)). In this approach, all BCV subjects are compared with all SoC subjects in the same stratum. Comparisons will be made based on the following hierarchy:
 - Alive or dead at Week 16
 - If both die before Week 16, compare time to death
 - If both are alive at Week 16, compare AAUC

Each comparison yields a favorable, unfavorable, or neutral result. The “proportion in favor of treatment” (Δ) is the net difference between the number of favorable pairs and the number of unfavorable pairs divided by the total number of pairs. The null hypothesis $H_0: \Delta=0$ is tested using a randomization test.

Another important factor that may influence the primary inference is the imputation of undetectable and BLQ AdV viremia values, with additional sensitivity analyses conducted in order to assess the potential impact of this imputation:

- Impute all undetectable/BLQ values at 1 copy/mL (i.e., 0 log₁₀ c/mL)
- Impute all undetectable/BLQ values at 189 copies/mL
- Impute all values < 1000 copies/mL at 1 copy/mL

In addition, a supportive analysis of overall mortality (adjusting for advanced baseline disease, [Matthes-Martin 2008](#)) will examine the non-inferiority of BCV treatment to SoC. No negative impact on mortality will be concluded if the upper bound of the one-sided 95% confidence

interval (CI) for the absolute difference between BCV mortality and SoC mortality is $< 10\%$. The proposed sample size will have $> 80\%$ power to demonstrate this conclusion, assuming SoC mortality in the expected range of 20% to 30% and a risk difference of 6% to 9% in favor of BCV (Feghoul 2015, Hiwarkar 2017, Mynarek 2014). In the event this supportive analysis concludes non-inferiority and the primary endpoint is met, superiority for overall mortality at Week 16 will be tested at alpha 0.05. Non-relapse mortality will be assessed in a similar fashion.

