4.4. Benefit:Risk Assessment

There is no approved therapy for the treatment of AdV infection. The current SoC may include reducing immunosuppression or off-label use of IV CDV; ribavirin is not recommended by ECIL and is rarely used. The efficacy of IV CDV for the treatment of AdV viremia in HCT recipients has not been formally established, with some reports in the literature describing high success rates in controlling viremia and others describing very poor response rates ([Ganapathi 2016](#), [Lion 2014](#)). The ECIL Treatment Guidelines note that while pre-emptive treatment of AdV with CDV has been reported in several studies, the “evidence concerning the effectiveness on mortality is inconsistent,” with AdV-related mortality rates varying from 23% to 50% despite pre-emptive treatment, and an AdV-related mortality of 18% has been reported for patients not receiving pre-emptive therapy ([Matthes-Martin 2012](#)).

Hiwarkar and colleagues have recently reported their experience with oral BCV, obtained via the NPP ([Hiwarkar 2017](#)). They compared virologic response amongst BCV recipients (generally applied in the setting of IV CDV contraindications or failure of IV CDV therapy) vs. those that were treated with IV CDV, as shown in [Figure 7](#).

Figure 7: Virologic Responses after BCV or CDV Treatment in Pediatric HCT Recipients

[figure not shown]
Abbreviations: ADV = adenovirus.
Source: [Hiwarkar 2017](#).

Rapid virologic response in pediatric HCT recipients (defined by the authors as $\geq 2 \log_{10}$ copies/mL decline in AdV viremia at two weeks) was more common with oral BCV (13/18, 72%) when compared with IV CDV (2/23, 9%). Patients were treated until viremia cleared; the median time to clearance of viremia with BCV was 4 weeks (range: 2 to 9 weeks) compared with 9 weeks (range: 3 to 15 weeks) with IV CDV ($p < 0.005$). The rapid antiviral response reported in these cohorts is consistent with the responses observed in interventional clinical trials with BCV (see Section 4.3.7 and the BCV Investigator's Brochure for more details). Furthermore, the lymphocyte count at the time of resolution of viremia was lower in patients receiving BCV than for those who received CDV. It is also noteworthy that many of the BCV patients had previously failed CDV.

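### The primary ANCOVA names no safeguard against unequal variances under 2:1 allocation, so its confidence interval could be too narrow or too wide; a robust standard error would remove the question at almost no cost.

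*Combined protocol and SAP*

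**What the plan says.** Section 12.4.1 specifies an "analysis of covariance (ANCOVA) with all stratification factors included in the model". The covariates are T cell-depletion method, time from HCT, and baseline viremia as a continuous log10 value. Undetectable results are set to 99 copies/mL. Section 12.4.2 applies the same method to continuous secondary endpoints, which include the AAUCs at Weeks 2, 4, 6 and 12.

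The synopsis plans 2:1 allocation, "with 94 subjects randomized to the BCV arm and 47 subjects randomized to the SoC arm". Section 12.1 bases power on one SD, "Assuming the observed standard deviation of 1.03" log10 copies/mL, observed "in AAUC at Week 16 from a comparable subset of SoC subjects". No SD for BCV-treated subjects appears.

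The sensitivity analyses in section 12.4.1 deal with deaths, drop-outs and the imputation of undetectable or unquantifiable values. None addresses unequal spread between arms. The generalized pairwise comparison uses a randomization test, but it estimates a different quantity. Section 12 leaves further detail to the SAP; the statistical text available here names no variance estimator and no check of residual variance.

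**The concern.** A pooled residual variance is right when both arms have the same spread. With unequal arm sizes and unequal spread, the model-based standard error is wrong, and the direction depends on which arm is more variable. If it is the smaller arm, the pooled variance is dominated by the 94 less variable subjects while the real uncertainty comes mostly from the other 47, so the SE is too small. If it is the larger arm, the SE is too large.

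There are reasons to think SoC may be the more variable arm. An arm that clears early is compressed toward the floor of log10(99), about 2.0. In the cohort comparison in section 4.4, "the median time to clearance of viremia with BCV was 4 weeks (range: 2 to 9 weeks) compared with 9 weeks" with IV CDV, for which the range was 3 to 15 weeks. Section 4.3.5 adds that IV CDV dose, regimen and duration are not standardized. What is at stake is whether the 95% CI for the primary treatment difference has its stated coverage.

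**Working it through.** **Inputs.** n = 94 and 47 (synopsis). SoC SD 1.03 and difference 0.6 (section 12.1). Two-sided alpha of 0.05 is assumed, since the documents state alpha only for the mortality superiority test. The BCV SD is also an assumption and is varied below.

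**The plan's own figure.** With a common SD of 1.03:

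- SE = 1.03 × √(1/47 + 1/94) = 0.184
- 0.6/0.184 = 3.26
- normal-approximation power = Φ(3.26 − 1.96) = 90.3%

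The noncentral t gives 89.9%. The stated power ("the study has > 90% power with the currently planned sample size") and the total of 141 are reproduced, on the premise that both arms share the SoC SD.

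**Effect of unequal SDs.**

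- Pooled variance = (46 × s_SoC² + 93 × s_BCV²)/139
- Model SE = √[pooled variance × (1/47 + 1/94)]
- True SE = √(s_SoC²/47 + s_BCV²/94)
- Approximate coverage = 2Φ(1.977 × model SE/true SE) − 1

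Worked for BCV SD 0.8:

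- pooled variance = (46 × 1.0609 + 93 × 0.64)/139 = 0.779
- model SE = √(0.779 × 0.0319) = 0.158
- true SE = √(1.0609/47 + 0.64/94) = 0.171
- ratio 0.920, coverage about 93.1%

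The last two columns come from 20,000 simulated trials per row. They use the ANCOVA with its three covariates and a true mean difference of zero.

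| Assumed BCV SD | Model SE | True SE | Ratio | Approx. coverage | Rejection, model SE | Rejection, HC3 |
|---|---|---|---|---|---|---|
| 1.2 | 0.2048 | 0.1947 | 1.052 | 96.2% | 4.0% | 4.6% |
| 1.03 | 0.1840 | 0.1840 | 1.000 | 95.2% | 4.7% | 4.3% |
| 0.9 | 0.1688 | 0.1766 | 0.956 | 94.1% | 6.1% | 4.8% |
| 0.8 | 0.1577 | 0.1714 | 0.920 | 93.1% | 6.8% | 4.6% |
| 0.7 | 0.1472 | 0.1667 | 0.883 | 91.9% | 8.4% | 4.7% |
| 0.6 | 0.1374 | 0.1625 | 0.846 | 90.5% | 9.8% | 5.0% |

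The coverage formula treats the SE as known, which is why it gives 95.2% rather than 95% at equal SDs. With 1.96 in place of 1.977 the 0.6 row reads 90.3%.

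Coverage depends only on the ratio of the two SDs. It therefore does not matter that 1.03 is not described as baseline-adjusted and that the ANCOVA residual SD may be smaller.

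**Cost of a robust SE.** At equal SDs the average simulated SE was 0.1893 with HC3 and 0.1857 with the model, a ratio of 1.02. Unequal-variance (Welch) power at a difference of 0.6 is 89.7% at equal SDs, against 89.9% for the pooled t test. It is 91.9% to 95.3% for BCV SD 0.9 to 0.6.

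**The case against.** The strongest reply is that the harmful ordering is not established. No section says SoC will be the more variable arm. The protocol's own BCV data describe a mixed arm rather than one bunched at the floor. In CMX001-304, among pediatric HCT recipients still on study, 59% were undetectable by Week 4 and 68% by Week 6, leaving 41% and 32% who were not (section 4.3.3.1). Even below 5 log10, 28% had not cleared within 4 weeks (section 4.3.3.2). In the subset of that study chosen to illustrate the endpoint, 28% died by Week 16 (section 4.3.7), which truncates AAUC.

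An illustrative trajectory model shows how much this matters. Its assumptions are a baseline mean of 4 log10 with SD 0.8, mean clearance of 4 versus 9 weeks, the 99 copies/mL floor, and truncation at death. It gives SoC residual SDs of 0.85 to 0.91. For BCV it gives 0.64 with 10% non-responders, 0.83 with 20%, 0.94 with 30% and 1.01 with 40%. Putting SoC at 0.88 into the coverage formula gives 92.5%, 94.7%, 95.7% and 96.2%. The shortfall nearly disappears at 20% non-response and reverses at 30%. This part of the objection stands. A reader might infer from the floor and the clearance times that the interval will be too narrow, but the documents do not support that prediction. The clearance times come from a non-randomized comparison of 18 BCV and 23 IV CDV patients, and SoC here is wider than IV CDV.

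A reader might also infer that the primary test has an inflated type I error. That is not supported for the mechanism at issue. If BCV clears faster, that is itself a treatment effect. With no effect on any subject, both arms share one distribution and the 5% test is valid. The rejection rates above 5% in the table need equal means together with unequal spread, which faster clearance alone does not produce.

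That the SAP may hold more detail is fair, and the point falls away if it already names a robust estimator. The listed sensitivity analyses do not fill the gap.

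**Conclusion.** The point holds as a conditional one. The plan states no protection against unequal variances for its primary estimate, and 2:1 allocation makes that estimate sensitive to them. If SoC is the more variable arm, with SD ratios from 1.14 (1.03/0.9) to 1.72 (1.03/0.6), coverage of the 95% CI would be about 94% to 90.5%. If BCV is more variable (SD 1.2), it would be about 96%. At equal SDs nothing is lost. Every BCV SD here is an assumption. The concern is CI coverage and the test of equal means when spreads differ. The stated power and sample size are not in question. Because the ordering cannot be known in advance, the sensible choice is an estimator that does not depend on it.

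**What to change.** In section 12.4.1, keep the ANCOVA, its covariates and its point estimate. Add one sentence basing the test and 95% CI for the treatment difference either on HC3 heteroscedasticity-robust standard errors or on arm-specific residual variances with Satterthwaite degrees of freedom. Name one of the two. Say in section 12.4.2 that the secondary AAUC endpoints use the same estimator.

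The cost is one sentence and one software option, with an SE about 2% larger if the variances are equal, and no extra subjects. It should be settled before database lock, after which section 12 allows no SAP amendment, and preferably early, since in an open-label trial a late choice of variance estimator would invite criticism.
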